2.1.3 Secondary endpoint

The following parameters will be determined:

(Part 1 & 2) Assessment of the pharmacokinetics of a single intravenous or oral dose of BI 1265162 (C-14) by means of the following parameters for total (C-14) BI 1265162-radioactivity, BI 1265162 and metabolite M582 (1) in plasma:

- AUC_{0-tz} (area under the concentration-time curve of the analyte in plasma over the time interval from 0 to the last quantifiable data point)
- C_{max} (maximum measured concentration of the analyte in plasma)

(Part 1 & 2) Evaluation of safety and tolerability of a single intravenous or oral dose of BI 1265162 (C-14) by means of

Proprietary confidential information © 2020 Boehringer Ingelheim International GmbH or one or more of its affiliated companies

- Percentage of subjects with drug related adverse events (AEs) including clinically relevant findings from the physical examination

2.2 FURTHER OBJECTIVES AND FURTHER ENDPOINTS

2.2.1 Further objectives

(Part 1 & 2) The evaluation of further pharmacokinetic, mass balance and tolerability parameters after a single intravenous or oral dose of BI 1265162 (C-14).

2.2.2 Further endpoints

2.2.2.1 Further pharmacokinetic endpoints

The following pharmacokinetic endpoints after a single intravenous and oral dose of BI 1265162 (C-14) will be calculated for total (C-14) BI 265162-radioactivity, BI 1265162 and its metabolite(s) in whole blood, plasma, urine and faeces (as feasible and appropriate), and may include

- $AUC_{t_1-t_2}$ (Area under the concentration-time curve of the analyte in plasma over the time interval from time point t_1 to t_2)
- $AUC_{0-\infty}$ (Area under the concentration-time curve of the analyte over the time interval from 0 extrapolated to infinity)
- $\%AUC_{t_2-\infty}$ (the percentage of $AUC_{0-\infty}$ obtained by extrapolation)
- t_{max} (time from dosing to maximum measured concentration of the analyte)
- λ_z (terminal rate constant)
- $t_{1/2}$ (terminal half-life of the analyte)
- MRT_{po} (mean residence time of the analyte in the body after oral administration)
- MRT_{iv} (mean residence time of the analyte in the body after IV administration)
- CL/F (apparent clearance of the analyte in the plasma after extravascular administration)
- CL (apparent clearance of the analyte in the plasma after intravascular administration)
- V_z/F (apparent volume of distribution during the terminal phase after extravascular administration)
- Ae_{urine, t_1-t_2} (amount of analyte that is eliminated in urine from the time interval t_1 to t_2)

Proprietary confidential information © 2020 Boehringer Ingelheim International GmbH or one or more of its affiliated companies

- $Ae_{urine, 0-t2}$ (amount of analyte that is eliminated in urine over the time interval from 0 to the last quantifiable time point)
- $fe_{urine, t1-t2}$ (fraction of administered drug excreted in urine from time point t1 to t2)
- $Ae_{faeces, t1-t2}$ (amount of analyte that is eliminated in faeces from the time interval t1 to t2)
- $Ae_{faeces, 0-t2}$ (amount of analyte that is eliminated in faeces over the time interval from 0 to the last quantifiable time point)
- $fe_{faeces, t1-t2}$ (fraction of administered drug excreted in faeces from time point t1 to t2)
- $CLR, t1-t2$ (renal clearance of the analyte in plasma from the time point t1 to t2)

Further pharmacokinetic parameters may be calculated as appropriate.

Determination of the metabolic pattern of BI 1265162 in plasma, urine and faeces after administration of BI 1265162 given intravenously (Part 1) and orally (Part 2) including structure elucidation of the metabolites (performed by AMS and classical methods; to be reported separately outside this report).

2.2.2.2 Further mass balance endpoints

Mass balance assessments

The following endpoints will be determined for urine:

- Ae (C-14)-radioactivity
- $\%Ae$ (fe) (C-14)-radioactivity
- Cum Ae : cumulative recovery of (C-14)-radioactivity
- Cum $\%Ae$ (fe): cumulative recovery of (C-14)-radioactivity expressed as a percentage of the dose

For faeces:

- Ae (C-14)-radioactivity
- $\%Ae$ (fe) (C-14)-radioactivity
- Cum Ae : cumulative recovery of (C-14)-radioactivity
- Cum $\%Ae$ (fe): cumulative recovery of (C-14)-radioactivity expressed as a percentage of the dose

Proprietary confidential information © 2020 Boehringer Ingelheim International GmbH or one or more of its affiliated companies

Mass balance recovery of (C-14)-radioactivity from all excreta:

- Ae (C-14)-radioactivity
- %Ae (fe) (C-14)-radioactivity
- Cum Ae: cumulative recovery of (C-14)-radioactivity
- Cum %Ae (fe): cumulative recovery of (C-14)-radioactivity expressed as a percentage of the dose

Further pharmacokinetic parameters may be calculated as appropriate.

2.2.2.3 Determination of the blood cell/ plasma and blood/ plasma ratios of (C-14)-radioactivity

The ratio of (C-14)-radioactivity in blood cells/ plasma (C_b / C_p) will be calculated according to the formula at those time points as indicated in the [Flow Chart](#).

$$C_{\text{bloodcells}} / C_{\text{plasma}} = \frac{C_{\text{blood}} - C_{\text{plasma}}(1 - HC)}{HC}$$

$C_{\text{blood cells}}$ = concentration in blood cells

C_{plasma} = concentration in plasma

C_{blood} = concentration in whole blood

HC = Haematocrit in decimal

Additionally, the ratio of concentration of (C-14)-radioactivity in blood and plasma ($C_{\text{blood}} / C_{\text{plasma}}$) will be calculated at all time points when (C-14)-radioactivity concentrations are quantifiable in blood and in plasma.

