5.3.2.4 Sampling of blood for haematocrit for blood cell/ plasma ratio

At each time point listed in the [Flow Chart](#), a blood sample will be taken. This blood will be used for measurement of haematocrit which is needed for determination of blood cell/ plasma ratio (see [Section 2.2.2.3](#)).

Haematocrit will be measured at

For a detailed description of blood sampling, sample volume, sample handling, sample preparation, sample storage, tube labelling and sample shipment, refer to the laboratory manual.

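### The blood cell/plasma ratio formula omits division by plasma concentration, so it returns the blood-cell concentration instead of the ratio

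*Protocol*

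**What the plan says.** Protocol section 2.2.2.3, under the further endpoints, commits to a specific calculation: "The ratio of (C-14)-radioactivity in blood cells/ plasma (C_b / C_p) will be calculated according to the formula". In plain notation the formula is

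C_cells / C_plasma = [C_blood − C_plasma·(1 − HC)] / HC.

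The symbols are defined beneath it. The three C terms are the "concentration in blood cells", the "concentration in plasma" and the "concentration in whole blood"; the remaining term is "HC = Haematocrit in decimal". A second quantity, C_blood/C_plasma, is to be reported wherever both are quantifiable.

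Protocol section 5.3.2.4 ties haematocrit sampling to this endpoint: haematocrit is the measurement "which is needed for determination of blood cell/ plasma ratio". Section 5.3.2.1 also lists the ratio among the purposes of blood and plasma sampling. Neither section gives another formula, and the readable SAP text does not restate or correct this one. SAP section 4 limits the analysis to Part 1 but still provides listings for all study endpoints.

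**The concern.** The two sides of the equation have different units. The left side is one concentration divided by another and has no unit. On the right side, concentrations are divided only by haematocrit, so the result is still a concentration. C_plasma appears to be missing from the denominator.

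If the formula is programmed as printed, the listed ratio is really the blood-cell concentration. It would fall as plasma radioactivity falls even when partitioning between cells and plasma is constant, which could be read as time-dependent uptake into blood cells. It would also disagree with the C_blood/C_plasma ratio reported beside it.

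**Working it through.** The plan gives no numerical result to reproduce, so the check is algebra, then units, then forward calculation. HC = 0.45 and the concentrations in steps 2 and 3 are illustrative assumptions, not trial estimates.

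**1. Algebra.** Whole-blood balance: C_blood = HC·C_cells + (1 − HC)·C_plasma.

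- Solve for cells: C_cells = [C_blood − (1 − HC)·C_plasma]/HC. This is the printed right-hand side.
- Divide by plasma: C_cells/C_plasma = [C_blood − (1 − HC)·C_plasma]/(HC·C_plasma). This is the ratio on the left-hand side.

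The two agree only when C_plasma = 1 in the chosen unit.

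**2. Forward calculation.** Fix a true ratio R, compute C_blood from the balance, then apply both formulas (concentrations in dpm/mL).

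| R | C_plasma | C_blood | Printed formula | Divided by C_plasma | C_blood/C_plasma |
|---|---|---|---|---|---|
| 0.1 | 20 | 0.45×2 + 0.55×20 = 11.9 | (11.9 − 11)/0.45 = 2 | 0.1 | 0.595 |
| 0.5 | 20 | 0.45×10 + 0.55×20 = 15.5 | (15.5 − 11)/0.45 = 10 | 0.5 | 0.775 |
| 1.0 | 20 | 0.45×20 + 0.55×20 = 20 | (20 − 11)/0.45 = 20 | 1.0 | 1.000 |
| 0.5 | 10 | 0.45×5 + 0.55×10 = 7.75 | (7.75 − 5.5)/0.45 = 5 | 0.5 | 0.775 |

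Rows 2 and 4 have the same partitioning and the same C_blood/C_plasma, yet the printed result halves with C_plasma. The same pattern holds for HC of 0.40, 0.45 and 0.50 and C_plasma from 1 to 1000: the printed formula always returns C_cells, and the corrected one always returns R.

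**3. Dependence on the unit.** Take C_blood = 80, C_plasma = 100, HC = 0.45.

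- Printed formula: (80 − 55)/0.45 = 55.6.
- Corrected: 55.6/100 = 0.556.
- Divide all concentrations by 60 (dpm to Bq): printed 55.6/60 = 0.926; corrected still 0.556.

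**4. Effect over the sampling schedule.** Flow Chart 1 has haematocrit measurements (footnote 8) and PK blood samples at both 2 h and 48 h, 46 h apart. Protocol Appendix 10.1 uses half-lives of 63 h for total radioactivity and 15.5 h for parent drug. Assuming mono-exponential decline and constant partitioning:

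- 63 h: 2^(−46/63) = 0.60, so the printed value falls by about 40%.
- 15.5 h: 2^(−46/15.5) = 0.13, so it falls by about 87%.

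The true ratio would not change. These two figures bracket an illustration; they do not predict the trial's plasma curve.

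**The case against.** The strongest case on the other side concerns importance, not algebra.

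- **Limited role.** The ratio is a further endpoint. Primary recovery, secondary AUC and C_max, the release criteria and the separate C_blood/C_plasma ratio do not use it. Only the seven Part 1 subjects are analysed, and descriptively. This stands and lowers the priority.
- **Clear intent and full reversibility.** The heading, sentence and left-hand side all say ratio, and a pharmacokineticist may divide by C_plasma without being told. The right value can always be recovered as [C_blood/C_plasma − (1 − HC)]/HC. This also stands: no data are lost. It is less sure that the error would be noticed, because in some units the wrong value looks like a plausible ratio (0.926 for 0.556 in step 3).
- **Unseen specifications.** Parts of the SAP are redacted, and PK calculations follow sponsor procedures outside these documents, so the formula may be correct there. That is possible, but nothing readable overrides the protocol's instruction.
- **Conversion loss.** A symbol could have dropped out when the PDF was converted to text. The equation is complete and well formed with no gap, so this is unlikely; a look at the signed PDF settles it. Amendment 1 lists section 2.2.2.3 among the sections corrected, but the current text still has the mismatch.
- **Haematocrit samples.** The footnote 8 draws also measure potassium for safety, so they have a purpose beyond this ratio. This is correct.

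**Conclusion.** The concern holds. By the protocol's own definitions, the formula in section 2.2.2.3 returns the blood-cell concentration and labels it as the cell/plasma ratio. The error factor is exactly C_plasma in the unit used, so it varies by subject, time point and unit. The algebra rests only on whole blood being cells plus plasma with haematocrit as the cell fraction; the numerical sizes above are illustrative.

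The consequence is confined to one further endpoint. No primary or secondary result is affected, and any wrong values can be recomputed from the same samples. It is a definite error of modest priority that should be corrected before the Part 1 ratios are listed or interpreted.

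**What to change.** Replace the formula with

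C_cells / C_plasma = [C_blood − C_plasma·(1 − HC)] / (HC·C_plasma),

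or equivalently [C_blood/C_plasma − (1 − HC)]/HC. The second form allows a direct check against the blood/plasma ratio listed alongside.

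First check the equation in the signed PDF. Because the trial stopped after Part 1, the correction matters most in the PK programming specification and the clinical trial report: state the formula used in both, and confirm that any ratios already produced were divided by C_plasma. If they were not, recompute them. The cost is a one-line correction and, at most, a rerun of one listing; no new samples or data are needed.

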2.2.2.4 Local tolerability

(Part 1) Local tolerability will be assessed by the investigator on the basis of swelling, induration, heat, redness, pain, and other findings.

(Part 2) Not applicable.

2.2.2.5 Further safety and systemic tolerability endpoints

[figure not shown]
[figure not shown]
- Safety laboratory tests
- 12-lead electrocardiogram (ECG), and
- Vital signs (blood pressure [BP], pulse rate [PR])
- Physical examination

Proprietary confidential information © 2020 Boehringer Ingelheim International GmbH or one or more of its affiliated companies

3. DESCRIPTION OF DESIGN AND TRIAL POPULATION

3.1 OVERALL TRIAL DESIGN AND PLAN

The overall trial design is depicted in [Figure 3.1: 1](#) and [Figure 3.1: 2](#).

The trial will consist of two trial parts, after the BI 1265162 (C-14) administration of single (Part 1) intravenous and (Part 2) oral doses. Both parts will be performed as a non-randomized, open-label, single-dose, single arm, trial in healthy male subjects in order to investigate by means of mass balance recovery (Part 1) metabolism (metabolic profile) and routes of elimination of (C-14) BI 1265162 after intravenous administration of 50 µg BI 1265162 (C-14) and (Part 2) the extent of oral absorption, metabolism (metabolic profile),

Proprietary confidential information © 2020 Boehringer Ingelheim International GmbH or one or more of its affiliated companies

and routes of elimination of (C-14) BI 1265162 after oral administration of 5 mg BI 1265162 (C-14). For details, see [Section 4.1](#).

Since in both parts different subjects will take part, there will be no washout period.

On Day 1, subjects will receive the (C-14)-labelled drug substance and will then stay in the trial centre up to the morning of Day 9 for collection of blood, urine, and faeces samples. Subjects will be readmitted to the trial centre for 24 hour collection intervals of urine and faeces on Days 15, 22, 29, and 36, if release criteria as specified below have not been met on Day 9 or during any subsequent 24-h collection visits. Within 24 hours before each of these once-weekly in-house collection intervals, subjects are to collect faeces at home. This 24 hour interval home collection faeces will be used for analysis in case no defecation occurs in the subsequent 24 hours in-house collection interval. Otherwise it will be discarded.

For determination of whether release criteria have been reached for individual subjects, (C-14)-radioactivity will be measured in excreta (urine and faeces) as well as in plasma. The actual recovery results will be reported as a percentage of the administered dose.

If one of the following release criteria is true, 24 hour collection intervals after Days 9, 16, 23, 30, or 37, (whichever is applicable) will not be performed:

- Greater than or equal to 90% of the administered dose has been recovered in urine and faeces combined over the investigational period, or
- If <1% of the dose administered has been collected in urine and faeces within 2 separate, consecutive 24 hour intervals, and
- Concentration of total radioactivity in plasma <5% of C_{max} of total radioactivity in plasma.

An overview of all relevant trial activities is provided in the [Flow Charts](#). For visit schedule and details of trial procedures at selected visits, see [Sections 6.1](#) and [6.2](#), respectively.

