7. All stools (for (C-14) BI 1265162 -radioactivity and metabolic profiling) will be collected quantitatively in portions up to 192 hours (sampling intervals of 0-24, 24-48, 48-72, 72-96, 96-120, 120-144, 144-168,168-192 hours) after administration of BI 1265162 (C-14). Thereafter 24-h collections are to be performed on Days 14-16, 21-23, 28-30, and 35-37. A blank sample will be collected before drug administration on Day -2, Day -1 or Day 1 (see [Section 5.3.2.6](#)). Faeces sampling for (C-14) BI 1265162 -radioactivity assessment will be stopped when the release criteria for radioactivity recovery (see [Section 3.1](#)) have been met (earliest stopping on Day 9). “+” means end of last collection interval, start of following collection interval. For details on sample usage, see [Section 5.3.2.6](#).
8. Measurement of haematocrit and potassium, only.
9. AEs and concomitant therapies will be recorded throughout the trial. At 1:05, 2 , 4 , 8, 24, 48, 192h after the infusion, local tolerability will be assessed according to the criteria put down in [Section 2.2.4](#).
10. End-of-trial (EoT) examination to be performed after last discharge from the trial centre, or, if all once-weekly 24-hour sampling periods are needed, after discharge on Day 37. EoT examination includes physical examination, vital signs, ECG, safety laboratory, recording of AEs and concomitant therapies.
11. The planned times for admission, discharge, start and end of the urine and faeces collection intervals are approximate. The procedures are to be performed within a time window of +/- 4 hours to the planned time.
12. Subjects are to collect faeces at home within 24-hour intervals before admission to once-weekly in-house collection intervals. Home collection intervals: Days 14-16, 21-23, 28-30, and 35-37. If faeces are collected in the subsequent in-house collection interval, faeces collected at home will be discarded. If no faeces is collected in the subsequent in-house collection interval (no defecation), faeces collected at home will be used instead for analysis.
13. For definition of the individual subject's end of trial, see [Section 6.2.3](#).
14. Subjects will collect a pre-dose faeces sample at home or at the site in specific containers provided by [REDACTED]

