2.1.2 Primary endpoints

The following parameters will be determined:

(Part 1 & 2) Mass balance recovery of total (C-14) BI 1265162-radioactivity in urine and faeces (and vomit, if applicable). Amount of radioactivity excreted as a percentage of the administered single intravenous or oral dose of BI 1265162 (C-14) in

- Urine - $fe_{urine, 0-t2}$ (fraction of (C-14)-radioactivity excreted in urine as percentage of the administered dose over the time interval from 0 to the last quantifiable time point)
- Faeces - $fe_{faeces, 0-t2}$ (fraction of (C-14)-radioactivity excreted in feaces as percentage of the administered dose over the time interval from 0 to the last quantifiable time point)
- Vomit - $fe_{vomit, 0-t2}$ (fraction of (C-14)-radioactivity excreted in vomit as percentage of the administered oral dose over the time interval from 0 to the last quantifiable time point) - if feasible and appropriate

The timeframe for determination of these endpoints depends on the time of discharge of each subject, based on radioactivity excretion, and is predicted to vary between 9 and 38 days after drug administration.

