7.3 PLANNED ANALYSES

Analysis sets

Statistical analyses will be based on the following analysis sets:

- Treated set (TS): The treated set includes all subjects who were entered and treated with one dose of trial drug. The treated set will be used for safety analyses.
- Pharmacokinetic parameter analysis set (PKS): This set includes all subjects from the treated set (TS) who provide at least one pharmacokinetic endpoint that was defined as primary or secondary and was not excluded due to a protocol deviation relevant to the evaluation of pharmacokinetics or due to pharmacokinetic non-evaluability (as specified in the following subsection ‘Pharmacokinetics’). Descriptive analyses of pharmacokinetic parameters will be based on the PKS.

Adherence to the protocol will be assessed by the trial team. Important protocol deviation (iPD) categories will be specified in the Integrated Quality and Risk Management Plan, iPDs will be identified no later than in the Report Planning Meeting, and the iPD categories will be updated as needed.

Proprietary confidential information © 2020 Boehringer Ingelheim International GmbH or one or more of its affiliated companies

Pharmacokinetics

Pharmacokinetic parameters listed in [Section 2.1](#) for drug (C-14) BI 1265162 will be calculated according to the relevant SOP of the Sponsor ([001-MCS-36-472](#)).

Plasma, urine and faeces concentration data and parameters of a subject will be included in the statistical pharmacokinetic analyses if they are not flagged for exclusion due to a protocol deviation relevant to the evaluation of pharmacokinetics (to be decided no later than in Report Planning Meeting) or due to pharmacokinetic non-evaluability (as revealed during data analysis, based on the criteria specified below). Exclusion of a subject's data will be documented in the CTR.

Relevant protocol deviations may be

- Incorrect trial medication taken, i.e. the subject received at least one dose of trial medication the subject was not assigned to
- Incorrect dose of trial medication taken
- Use of restricted medications

Plasma and urine concentrations and/ or parameters of a subject will be considered as non-evaluable, if for example

- Missing samples/ concentration data at important phases of pharmacokinetic disposition curve

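### The low-excretion release criterion does not require that a stool was passed, so two stool-free days can help stop faecal collection before excretion is complete

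*Protocol*

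**What the plan says.** Protocol Section 3.1 introduces the release rule with "If one of the following release criteria is true, 24 hour collection intervals after Days 9, 16, 23, 30, or 37" and then lists three bullets:

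- Limb A: "Greater than or equal to 90% of the administered dose has been recovered in urine and faeces combined over the investigational period, or"
- Limb B: "If <1% of the dose administered has been collected in urine and faeces within 2 separate, consecutive 24 hour intervals, and"
- Limb C: "Concentration of total radioactivity in plasma <5% of C_{max} of total radioactivity in plasma"

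The rule governs the primary endpoint's data. Flow Chart footnote 7 says: "Faeces sampling for (C-14) BI 1265162 -radioactivity assessment will be stopped when the release criteria for radioactivity recovery" have been met, with Day 9 as the earliest stop. Section 2.1.2 adds: "The timeframe for determination of these endpoints depends on the time of discharge of each subject, based on radioactivity excretion".

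The protocol foresees an interval without defecation, but only for the weekly visits from Day 14 on. There, "home collection faeces will be used for analysis in case no defecation occurs in the subsequent 24 hours in-house collection interval". The in-house stay to 192 h has no counterpart. Exclusion criterion 26 turns away men who average less than one bowel movement every other day.

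On evaluability, Section 7.3 (repeated in SAP Section 6.3) reads: "Plasma and urine concentrations and/ or parameters of a subject will be considered as non-evaluable, if for example". That sentence does not name faeces.

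**The concern.** Limb B is meant to show that excretion has nearly ended. It is computed from what was collected, so a day without a stool contributes nothing from the faecal route, which the protocol's own planning figures put at 85% of an intravenous dose. Low collection can then mean low excretion or simply a stool not yet passed, and the rule does not separate the two. Limb C looks at plasma and can be satisfied while label is still leaving through the gut.

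At stake is whether a subject's collection is stopped correctly, and whether a reader of the Part 1 report can tell a recovery that is truly low from one with an outstanding stool. A second, smaller matter is wording. The three bullets are joined by a mixed 'or' and 'and' under a lead-in saying that one of them suffices, and the text does not say whether the 1% applies to each interval or to both together.

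**Working it through.** **Inputs.** The half-life of total radioactivity is 63 h and the split is 85% faeces, 15% urine. Both come from the worst-case dosimetry in Appendix 10.1. The half-life reproduces: 15.5 / 7.4 × 30 = 62.8 h. Assumption: no stool in 144-192 h, the last two in-house intervals. All results are illustrations, not forecasts.

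**Limb B, single exponential.** Fraction remaining R(t) = 2^(−t/63): R(144) = 0.2051, R(168) = 0.1575, R(192) = 0.1209.

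- Urine 144-168 h: 0.15 × (0.2051 − 0.1575) = 0.71% of dose.
- Urine 168-192 h: 0.15 × (0.1575 − 0.1209) = 0.55%.
- Read per interval, limb B is met. Read combined, 1.26% fails.
- Across all half-lives, urine in 144-168 h peaks at 0.85% (near 108 h), so with a 15% urinary share the per-interval reading is always met.

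**Limbs A and C, single exponential.** Plasma at 192 h, 191 h after the infusion ends, is 2^(−191/63) = 12.2% of Cmax, so limb C blocks release. Limb C passes only if the half-life is below 191 / log2(20) = 44.2 h. Recovery without the stool, 1 − R(192) − 0.85 × (R(144) − R(192)), is at least 90% up to 44.9 h. Whenever limb C passes, limb A is already met, so there is no false release.

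**Two phases.** Protocol Section 3.2 calls elimination multi-exponential. After a 1-h infusion take C/Cmax = (1 − f)·2^(−(t−1)/Tf) + f·2^(−(t−1)/63), with excretion rate proportional to C. Then AUC/Cmax is D = (1 − f)/(1 − 2^(−1/Tf)) + f/(1 − 2^(−1/63)) hours. At late times the fraction remaining is f × 63/ln2 × 2^(−(t−1)/63) / D.

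Example, f = 0.2 and Tf = 1 h:

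- D = 1.6 + 18.28 = 19.88 h. Remaining at 144, 168 and 192 h: 0.1896, 0.1456, 0.1118.
- Plasma at 192 h: 0.2 × 12.2% = 2.4% of Cmax, so limb C is met.
- Urine: 0.66% and 0.51%, so limb B is met per interval.
- Stool missed: 0.85 × (0.1896 − 0.1118) = 6.6%. Recovery is 88.8% with the stool and 82.2% without.
- With the stool, excretion would be 4.4% and 3.4% per day and recovery below 90%, so collection should have continued.

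Over f = 0.05, 0.1, 0.2, 0.3, 0.4 and Tf = 0.5, 1, 2 h (15 points):

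- Plasma is 0.6-4.9% of Cmax, urine 0.42-0.70% then 0.32-0.54%, and recorded recovery 81.1-88.7%. All 15 are released on B and C if the 1% is per interval.
- At 11 points the decision is wrong: with the stool, recovery is 88.1-89.8%. Their combined urine is 1.06-1.24%, so the combined reading blocks all 11.
- At the other 4, recovery with the stool is 90.5-92.9%, so stopping would have been right. Their combined urine is 0.74-0.99%.
- Generally, a wrong decision needs a slow half-life above about 58 h per interval, or about 65 h combined. The protocol's 63 h lies between, so the unstated reading decides the outcome.

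**Edges of the grid.** Limb C blocks release once f exceeds 0.05 / 0.1223 = 0.41. At the other end, intravenous parent data (Table 1.3: 1, N = 4, preliminary) give AUC/Cmax = 2200 / 1880 = 1.17 h. Since D is at least (1 − f) + 91.4f, that caps f near 0.0019. Recovery without the stool is then about 97%, so limb A is met anyway.

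**What limb B itself costs.** The weekly windows starting at 336, 504, 672 and 840 h would add 0.58 + 0.09 + 0.01 + 0.00 = 0.7 points at 63 h. On a seven-subject mean that is 0.7 / 7 = 0.1.

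**Frequency of a 48-h gap (assumed).** It runs from near 0 with a strict alternate-day habit to exp(−1) = 37% with Poisson timing at 0.5 stools per day.

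**The case against.** Much of the case against stands.

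- A reader might charge the 4.2-7.0 points of unpassed stool (0.6-1.0 on the mean) to limb B. The documents do not support that. Everyone leaves on Day 9 and the next collection starts on Day 14, so a stool-free subject who fails limb B loses the same stool.
- A reader might take 11 of 15 as a risk. It is a count of chosen points. The ceiling f = 0.40 sits just under the 0.41 at which limb C blocks release, and the grid implies AUC/Cmax of 5.8-38.6 h against 1.17 h for parent drug. Parent is only a proxy, and the documents give no total-radioactivity profile to settle the matter.
- The 63 h is scaled from rats for a worst-case safety calculation. At the 15.5 h parent half-life, single exponential, recovery without the stool is about 99.9%.
- The recorded fraction is correct as the endpoint is defined, because an unpassed stool has not been excreted.
- Protocol Sections 2.2.2.1 and 2.2.2.2 define interval and cumulative recovery, and SAP Sections 4 and 7 promise endpoint listings and individual values. Most of the needed display is therefore planned.
- It would be too strong to say that no rule covers incomplete faeces. Section 7.3 allows faecal data to be flagged, its examples are partly not shown, and missing-data handling sits in sponsor manuals outside these documents.

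None of this supplies a stool condition in limb B, or shows that the planned listings will record which limb was met.

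**Conclusion.** Minor, with medium confidence. As written, limb B can be met on urine alone after two stool-free days. Limb C is a real safeguard but not an assured one: it blocks every such release under single-exponential loss and fails to do so under some two-phase profiles, such as a 63 h phase at about 5-40% of Cmax. Collection can then stop with about 81-89% recorded. The consequence is a false stop decision and an unlabelled incomplete faecal collection for that subject. It is not a material bias in mean recovery, since limb B withholds at most 0.7 points per subject and 0.1 on the mean at 63 h.

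This rests on the worst-case 63 h and 85/15 inputs, a per-interval reading of the 1%, excretion tracking plasma, and a stool-free gap of unknown frequency.

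A reader might infer from SAP Section 6.1, which reports every Part 1 subject discharged on Day 9, that early release occurred. That discharge was scheduled for all and does not show which limb anyone met. The documents do not show that the problem arose.

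**What to change.** For the Part 1 report, add two items to the recovery listings already planned: the release limb each subject met, and a 'faecal collection incomplete' label for anyone released on limb B with no stool in 144-192 h. Exclude nobody. Section 5.3.2.6 already has stool times recorded in the eCRF, so this needs no new data.

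If the rule is reused:

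- Let limb B count only when at least one stool was passed across the two consecutive intervals (not one in each). Otherwise carry the decision to the next scheduled collection.
- Write the rule as 'A, or (B and C)'.
- State whether the 1% is per interval or combined.

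The cost is a line of protocol text and an occasional extra weekly visit that recovers little. The change protects the stop decision. It does not recover stool passed between Day 9 and Day 14, so the label would still be needed.
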